Methods: A sample of 80 patients who are receiving fixed orthodontic treatment at UNC-Chapel Hill or at Selden Orthodontics in Charlotte, NC will be recruited to participate. Subjects will be assigned into one of four groups: 014 wire with twin brackets; 016 wire with twin brackets; 014 wire with self-ligating brackets; and 016 wire with self-ligating brackets. All subjects will be indirect-bonded following a digital Insignia setup reviewed and approved by the principal investigator. Intraoral scans taken as part of treatment before bonding, 6 weeks after bonding, and 12 weeks after bonding will be analyzed. From these scans, Little Index measurements and superimpositions will be completed to determine changes in alignment as well as translation and rotation of the teeth in three dimensions.

Specific Aims

The aim of this study is to study the effect of wire dimension, timing and ligation method on leveling and aligning in orthodontic treatment using 3D imaging.

Specifically to:

1. Analyze the effect of wire dimension (.014 vs. .016) and time-course (first six weeks or second six weeks) on Stage I treatment
2. Correlate clinical tooth movements with bench data for four types of malalignment
 - a. In-out
 - b. Rotation
 - c. Tip
 - d. Vertical step
3. Analyze effect of ligation method (twin vs. self-ligating) on Stage I treatment

These specific aims will serve to address this hypothesis: Archwire dimension affects tooth movement in Stage I of orthodontic treatment, depending upon:

1. Variation in constraining force;
2. Time-course due to force decay of superelastic wires; and
3. Method of ligation.

Significance

Many archwire dimensions are available to orthodontists for leveling and aligning, but little objective clinical evidence is available to indicate which archwire dimension is ideal for a given patient with an individual type and degree of malalignment during this stage. The effects of bracket type (twin vs. self-ligating) and time-course on this stage are similarly unclear.

Superelastic wires like NiTi and CuNiTi allow a light, continuous force to be maintained over an extended period of time and large range of deflection, which tends to make them the preferred archwires for Stage I treatment(1). Some clinicians believe that self-ligating brackets and thermoelastic wires like CuNiTi are more efficacious for leveling and aligning than twin brackets and superelastic wires. However, Fleming and Johansson have demonstrated no significant difference in the efficacy of traditional brackets compared with either active or passive self-ligating appliances(2, 3), and Pandis found the difference between laboratory and clinical settings appears to dispel any laboratory-based claims that Cu NiTi is superior(4). It is also unclear if one wire dimension is superior to others for Stage I treatment. When 014 and 016 NiTi archwires were tested by Montasser using multiple brackets *in vitro*, some combinations increased the correction while others decreased it(5). But there is even disagreement on how to measure that alignment. Macauley and Sjogren found that precision and accuracy are lacking in traditional measurement techniques for Little Index calculations(6,7). These measurements become more reliable, however, when digital models are used to reduce subjectivity in choosing contact points and increase precision in measuring contact point displacement(8). Whitecotton used these methods along with 3D superimposition to demonstrate in a pilot study that archwire dimension has an effect on the efficacy of alignment, and that the efficacy of alignment is time-dependent. During the first 12 weeks of treatment, 014 wires produced greater mesiodistal effects (distalization), while 016 produced greater vertical effects and in-out effects (extrusion and buccal movement, respectively). More distalization occurred during the first six weeks, while more extrusion and buccal movement occurred during the second six weeks(9). Benchtop tests have also shown that there is a critical point at which the deflection of a wire becomes large

enough that it can no longer slide through the brackets. Gibson and Ko have proposed the concept of “constraint” to describe the point at which the wire binds, creating a spring-like force similar to that of an open coil between neighboring teeth. In four types of malalignment (in-out, rotation, tip and vertical step), they found a critical value where the constraining force increases. This critical point is reached at different degrees of discrepancy in different malalignment types. Gibson and Ko hypothesized these differences may dictate efficiency of the alignment(10). However, the correlation between clinical data and constraining force on efficacy of alignment has not been performed.

Whitecotton’s study was relatively underpowered. The current study seeks to use an expanded sample size to investigate possible correlations with Gibson and Ko’s benchtop data and analyze the influence of wire dimension and timing on leveling and alignment. To our knowledge, no previous studies have used 3D imaging to compare twin and self-ligating brackets in Stage I of orthodontic treatment.

In a larger sense, we hope this study will help move orthodontics in the direction of personalized medicine. More specifically, we hope it will provide insight into which archwire dimension and ligation method is ideal for a given patient with an individual type and degree of malalignment.

Methods

With IRB approval, we plan to recruit 80 participants from the post-doctoral orthodontic clinic and the private practice of UNC orthodontic faculty member, [name], using notes and photographs from the initial records appointment to screen for exclusion and inclusion criteria.

- Inclusion:
 - Non-extraction treatment
 - Little Index of 1-15 mm
 - Presence of all permanent anterior teeth
 - Age 10-45 years
 - Consent to participate in the study.
- Exclusion:
 - Systemic diseases such as diabetes, hypertension, temporomandibular disorders (TMD), craniofacial syndrome, etc.
 - Spacing between anterior teeth
 - Subjects who have incisor mandibular plane angle (IMPA) greater than or equal to 100 degrees
 - Anterior tooth completely blocked from the arch form
 - Periodontal pocketing of any anterior teeth greater than 4mm

[figure not shown]

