After the scans are completed, we will calculate the differences in several numbers as they change from Time Zero to Time One to Time Two: Little's Index, calculated using the line measurement method; translation in three planes, calculated using the superimposition method; and rotation around three axes, calculated using the superimposition method. We'll then use 3-way ANOVA to evaluate the effect of 3 factors: wire dimension, time, and ligation method. We will also use a repeated measure linear regression model to evaluate any correlation between the degrees of malalignment and the rate of tooth movement.

Possible Limitations

There are limitations to this study. It will be impossible to completely randomize bracket type (twin vs. self-ligation) because part of this study will be conducted in a post-doctoral orthodontic clinic where not all attending faculty members are comfortable using both self-ligating and twin brackets. Bracket type will thus be assigned according to faculty member preference.

Additionally, while we hope to have 80 patients complete all scans, it may be difficult to recruit 80 patients and keep scans at correct time intervals due to patient compliance with appointments. Bonding errors may also occur during indirect bonding appointments and cause bracket placement errors that negate the accuracy of the custom Insignia indirect-bonding jigs.

During the data analysis, contact point selection for the Little Index will be subjective even using digital models in the method described by Dowling(8). Point selection for the rigid movement (translation and rotation) portion of the study will be similarly subjective.

Timeline

- Fall 2017-Summer 2018: Data collection
- Fall 2018: Data and statistical analysis
- Spring 2019: Manuscript preparation

Human Subjects

IRB approval has not yet been obtained but will be before patient screening begins. There are no direct benefits to the patient for participating in the study, and there are no risks associated with participating in the study since we are just observing normal orthodontic treatment. The risks that are inherent in any orthodontic treatment (risks of discomfort, tooth mobility, root resorption, and allergic reactions) are neither increased nor decreased by participation in this study. There are no extra appointments necessary for participation in the study, and steps will be taken to de-identify all patient information and study data.

References

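### Ages 10 to 45 are pooled and no planned model includes age, which may cost precision for wire dimension and could bias twin v self-ligating

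*Combined protocol and SAP*

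**What the plan says.** The inclusion list under Methods gives the age criterion as "Age 10-45 years" and also requires "Presence of all permanent anterior teeth". No criterion concerns completed growth, and no age strata are defined. On numbers, "we plan to recruit 80 participants". The abstract adds that "Subjects will be assigned into one of four groups", formed by 014 or 016 wire with twin or self-ligating brackets. Patients come from a university post-doctoral clinic and one private practice.

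Under Data Analysis, the main method is "3-way ANOVA to evaluate the effect of 3 factors: wire dimension, time, and ligation method". The second is a "repeated measure linear regression model to evaluate any correlation between the degrees of malalignment and the rate of tooth movement". Age appears in neither. The outcomes are changes in Little's Index, translation in three planes and rotation about three axes.

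The two treatment factors are allocated differently. Methods has wires assigned through random-number IDs held by a third party. Possible Limitations says that bracket type depends on what faculty members prefer to use. That section does not mention age or growth.

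**The concern.** A sample that runs from 10-year-olds to adults of 45 may differ by age in tooth movement, either because teeth and jaws in the youngest are still changing or because the response to a given force varies with age. The plan holds each patient's age but does not use it.

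Three results could be touched:
- **Wire dimension.** Variation due to age stays in the residual, and an age difference that arises by chance between the 014 and 016 groups is left uncorrected.
- **Ligation.** Bracket type is not randomised. If the faculty members or settings that favour one bracket also treat younger patients, age is mixed with ligation in the third specific aim.
- **Absolute movement.** Significance reports from the pilot that 014 had the larger mesiodistal effects, "while 016 produced greater vertical effects and in-out effects (extrusion and buccal movement, respectively". There is no untreated comparison, so a report of how far teeth extruded or moved buccally could be read as the action of the wire when some of the movement in growing patients might have occurred anyway.

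**Working it through.** **The plan's own figure.** The sample size of 80 comes with no alpha, power, effect size or standard deviation, so it cannot be reproduced. For orientation, assume two-sided alpha 0.05, a 40 v 40 split (the documents give no ratio) and SD = 1. The standard error of a two-group contrast is √(2/40) = 0.224. The difference detectable with 80% power is (1.96 + 0.84) × 0.224 = 0.63 SD.

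**1. Precision of the wire contrast.** Let R² be the share of between-patient variance that age explains. The documents give no value. A patient-level model with four groups has 80 − 4 = 76 residual degrees of freedom, or 75 with an age term.

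Reduction in standard error = 1 − √[(1 − R²) × 76/75]

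Power at d = 0.63 = Φ(0.63 / [0.224 × √(1 − R²)] − 1.96), by normal approximation

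| R² assumed | Standard error shorter by | Power |
|---|---|---|
| 0 | −0.7% (slightly longer) | 80.4% |
| 0.02 | 0.3% | 81.2% |
| 0.05 | 1.9% | 82.4% |
| 0.10 | 4.5% | 84.4% |
| 0.20 | 10.0% | 88.3% |

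**2. What those R² values would require.** Suppose that age acts only as a shift of g SD over the 12 weeks in a share p of patients who are growing. The added variance is v = g²p(1 − p), and R² = v/(1 + v). With p = 0.5, R² = 0.10 needs v = 0.111, so g = √(0.111/0.25) = 0.67 SD. R² = 0.20 needs g = 1.0 SD. If the shift is ignored, power at d = 0.63 falls from 80.4% to 79.6% at g = 0.3, 78.0% at g = 0.5 and 71.2% at g = 1.0.

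**3. Bias in the wire contrast.** Under random allocation the expected bias is zero. The SD of the chance imbalance is g × √[p(1 − p) × 2/40], which is 0.011 at g = 0.1 and 0.056 at g = 0.5 (p = 0.5). In 4,000 simulated trials, with growth spread evenly over the two six-week periods, the mean error was −0.006 for wire and −0.001 for first v second period. Both are within simulation error.

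**4. Bias in the ligation contrast.** Here nothing balances age. Bias = g × difference in the share of growing patients between bracket groups. Type I error follows from bias/0.224.

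| g assumed | Difference in share growing, assumed | Bias | Type I error |
|---|---|---|---|
| 0.1 SD | 10 points | 0.01 SD | 5.0% |
| 0.3 SD | 30 points | 0.09 SD | 6.9% |
| 0.5 SD | 50 points | 0.25 SD | 20.1% |

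**The case against.** The strongest reply is that the size is unknown and may be small. The documents give no growth rate or age effect, follow-up is 12 weeks, and all permanent anterior teeth must be present, which narrows the eruption concern. In the two-class model a shift of up to 0.3 SD costs less than one point of power. This stands, and it means that the precision argument alone is modest.

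It is also fair to say that the specific aims are comparative or correlational. None of them attributes absolute extrusion or buccal movement to a wire, so the caution about absolute movement concerns how results are worded and does not reveal a fault in a planned test.

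A reader might infer three stronger things, which the documents do not support:
- **That growth is counted as wire-driven in the 014 v 016 comparison.** Wires are allocated by random number, so both groups share any growth in expectation.
- **That growth adds noise to every comparison.** First v second six weeks is a within-patient contrast, in which steady growth largely cancels if the pairing is kept. Little's Index measures displacement between contact points, so movement common to neighbouring teeth cancels there too.
- **That an age term would serve the hope of matching wire to patient.** Abstract and Significance frame that by type and degree of malalignment. An age main effect shifts both wires equally and does not show which wire suits which age; that would need a wire-by-age interaction.

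**Conclusion.** The point holds in a limited form. A wide age range is pooled, age is available, and no planned model uses it. For wire dimension there is no expected bias. The possible loss is precision, from almost nothing to about 10% of the standard error for R² between 0.02 and 0.20, together with chance imbalance that goes uncorrected. For twin v self-ligating, bias is possible. It ranges from negligible to 0.25 SD in the scenarios shown and depends on an age mix by bracket group that the documents do not give.

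Whether growth enters the translations at all depends on the superimposition reference, which the readable text does not name. So natural change in growing patients cannot be excluded, but it cannot be stated as fact either. All sizes rest on the assumed 40 v 40 split, the normal approximation and the assumed values of R², g and share growing. The change is worth making because it is nearly free.

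**What to change.** 1. Prespecify age at bonding as a patient-level covariate in the model for every outcome, including the malalignment regression, and fix its functional form before the data are seen.
2. State that patient is the repeated-measures unit in the main model. The plan says this of the regression but not of the ANOVA. Keeping the pairing is what lets steady growth cancel from the period contrast.
3. Report age by wire group and by bracket group, so that a reader can judge the ligation contrast. The age term is only partial protection there: other differences between faculty members and settings remain.
4. Do not describe absolute vertical or in-out movement as an effect of the wire alone.

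The cost is about one degree of freedom (a standard error 0.7% longer if age explains nothing), one descriptive table and a sentence of text. No new data or patients are needed.

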After the scans are completed, we will calculate the differences in several numbers as they change from Time Zero to Time One to Time Two: Little's Index, calculated using the line measurement method; translation in three planes, calculated using the superimposition method; and rotation around three axes, calculated using the superimposition method. We'll then use 3-way ANOVA to evaluate the effect of 3 factors: wire dimension, time, and ligation method. We will also use a repeated measure linear regression model to evaluate any correlation between the degrees of malalignment and the rate of tooth movement.

Possible Limitations

There are limitations to this study. It will be impossible to completely randomize bracket type (twin vs. self-ligation) because part of this study will be conducted in a post-doctoral orthodontic clinic where not all attending faculty members are comfortable using both self-ligating and twin brackets. Bracket type will thus be assigned according to faculty member preference.

Additionally, while we hope to have 80 patients complete all scans, it may be difficult to recruit 80 patients and keep scans at correct time intervals due to patient compliance with appointments. Bonding errors may also occur during indirect bonding appointments and cause bracket placement errors that negate the accuracy of the custom Insignia indirect-bonding jigs.

During the data analysis, contact point selection for the Little Index will be subjective even using digital models in the method described by Dowling(8). Point selection for the rigid movement (translation and rotation) portion of the study will be similarly subjective.

Timeline

- Fall 2017-Summer 2018: Data collection
- Fall 2018: Data and statistical analysis
- Spring 2019: Manuscript preparation

Human Subjects

IRB approval has not yet been obtained but will be before patient screening begins. There are no direct benefits to the patient for participating in the study, and there are no risks associated with participating in the study since we are just observing normal orthodontic treatment. The risks that are inherent in any orthodontic treatment (risks of discomfort, tooth mobility, root resorption, and allergic reactions) are neither increased nor decreased by participation in this study. There are no extra appointments necessary for participation in the study, and steps will be taken to de-identify all patient information and study data.

References

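### Little Index change is compared by 3-way ANOVA without the Time Zero value, so any severity difference between the preference-assigned bracket groups enters the ligation effect, and the randomised wire contrast loses precision

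*Combined protocol and SAP*

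**What the plan says.** The Data Analysis section defines the outcomes as changes between scans: "we will calculate the differences in several numbers as they change from Time Zero to Time One to Time Two". Little's Index is one of them, beside translations and rotations. The comparative analysis is to "use 3-way ANOVA to evaluate the effect of 3 factors: wire dimension, time, and ligation method". No covariate, stratification or matching on starting severity appears anywhere.

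A second model, a repeated-measures linear regression, is planned "to evaluate any correlation between the degrees of malalignment and the rate of tooth movement". Its terms are not listed, and it is not said to adjust the wire or ligation comparison.

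Four other statements bear on the point:

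- **Entry (Methods, inclusion criteria):** "Little Index of 1-15 mm".
- **Bracket allocation (Possible Limitations):** "Bracket type will thus be assigned according to faculty member preference".
- **Wire allocation (Methods):** wires carry identifiers from a random number generator run by a third party and are handed out blind. I read this as randomised.
- **Aim 3 (Specific Aims):** "Analyze effect of ligation method (twin vs. self-ligating) on Stage I treatment".

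The Time Zero scan is part of routine treatment, so the starting Little Index is available for every participant at no extra cost.

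**The concern.** Subtracting the baseline removes its influence only if expected change is unrelated to the starting value. That cannot be so here: a patient who starts at 1 mm can improve by at most 1 mm, and one who starts at 15 mm by up to 15 mm.

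The consequence differs between the two treatment factors.

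- **Ligation.** Nothing in the design balances severity between bracket groups. If the clinicians who prefer one bracket happen to treat more irregular cases, their patients have more index to lose, and the ANOVA on change could report that as a bracket effect.
- **Wire.** Randomisation balances severity in expectation, so leaving the covariate out does not bias the contrast. Variation in starting severity stays in the error term, however. That matters in a study that offers a larger sample as its answer to an underpowered pilot.

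**Working it through.** **Inputs.** From the documents: 80 patients, a permitted baseline of 1–15 mm, preference-based brackets and random wires. The documents give no SD, slope, alpha, power or group sizes, so there is no stated figure to reproduce. Everything below is illustrative and assumes:

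- one arch, 12-week change, two-sided 5% test
- fraction of irregularity resolved *p* = 0.4 or 0.6
- residual SD *e* = 1.0 or 1.5 mm
- baseline SD *s* = 2 mm, or 14/√12 = 4.04 mm (uniform spread over 1–15 mm)
- difference *d* in mean Time Zero index between bracket groups

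The model is change = *p* × baseline + error.

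**1. Ligation bias.** Shift = *p* × *d*. For *d* = 1 mm this is 0.4 to 0.6 mm. For *d* = 0 it is zero.

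**2. Ligation false-positive rate, no true effect.** The SD of change is √(*p*²*s*² + *e*²), and the rate comes from the noncentral t distribution. Example at *p* = 0.6, *e* = 1.0, *s* = 2:

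- SD = √(1.44 + 1.00) = 1.562 mm
- standard error at 40 v 40 = 1.562 × √(2/40) = 0.349 mm
- noncentrality = 0.6/0.349 = 1.72, giving a rate of 0.396

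| Difference, split | *s* = 2 mm | *s* = 4.04 mm |
|---|---|---|
| 1 mm, 40 v 40 | 18–40% | 13–17% |
| 0.5 mm, 40 v 40 | 8–14% | 7–8% |
| 1 mm, 60 v 20 | 15–31% | 11–14% |

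With the covariate, simulation gives about 5%, assuming an error-free baseline and the same slope in both bracket groups.

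**3. Improvement bounded by the starting value.** Here change = baseline × fraction corrected, with a beta-distributed fraction of mean 0.4 or 0.6 and SD 0.15 or 0.25. A difference of about 1 mm gives simulated false-positive rates of 12–39% (baseline SD about 2 mm) or 10–18% (near-uniform spread). With the covariate the rate is about 5%.

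**4. The two-period layout.** The plan has time as a factor, so I also simulated two six-week changes per patient analysed as if independent. Inputs were a 1 mm difference, 63% or 77.5% of irregularity retained per period, and period residual SD 0.7 or 1.0 mm. Ligation false positives were about 19–52%. For wire, with no true effect, they were about 4–13%. The wire excess comes from ignoring that the two periods share a patient, not from bias. A patient-level analysis with the Time Zero index returned both to about 5%.

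**5. Error in the baseline measurement.** The limitations concede that "contact point selection for the Little Index will be subjective even using digital models". With baseline error SD *u*, the bias left after adjustment has size (1 − *p*) × [1 − *s*²/(*s*² + *u*²)] × *d* and runs in the opposite direction: the more irregular group looks slightly worse. At *s* = 2 and *d* = 1 mm:

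- smallest: 0.4 × (1 − 4/4.25) = 0.02 mm (*p* = 0.6, *u* = 0.5)
- largest: 0.6 × (1 − 4/5) = 0.12 mm (*p* = 0.4, *u* = 1.0)

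At *u* = 1.0 mm, simulated false-positive rates are 14–29% unadjusted and about 6–7% adjusted.

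**6. Wire precision.** R² = *p*²*s*²/(*p*²*s*² + *e*²), and the sample equivalent is 1/(1 − R²). The difference detectable with 80% power is 2.80 × SD × √(2/40).

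- At *s* = 2: R² runs from 0.64/2.89 = 0.22 to 1.44/2.44 = 0.59, so the covariate is worth 1.28 to 2.44 times the sample. The detectable difference falls from 0.80–1.20 mm to 0.63–0.94 mm.
- Bounded model, baseline SD about 2 mm: 1.2 to 2.5 times.
- Bounded model, uniform 1–15 mm: 1.5 to 4.3 times, and the detectable difference falls from 1.32–2.07 mm to 0.84–1.40 mm.

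**The case against.** The strongest reply is that the ligation harm is hypothetical. The stated reason for preference-based assignment is that some faculty are not at ease with both bracket types. That is clinician familiarity, not selection by crowding, and everyone meets the same entry criteria. This stands as far as it goes: the documents show no severity difference, and without one there is no bias. But the plan has no protection if one arises, and disclosing non-random assignment is not an analytic remedy.

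A second reply is that this is a short thesis proposal: naming three factors does not rule out covariates, and the separate regression shows that severity is not ignored. The regression does show that the authors think severity may matter. As described, though, it serves a different question and leaves both treatment contrasts unadjusted.

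A third is that the main figures use a single 12-week change, not the two-period ANOVA, and an error-free baseline. Both points are fair. Modelling two periods as independent raises the ligation error rates. Baseline error narrows the contrast with the adjusted analysis but does not remove it.

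Finally, Little Index is one of seven quantities to be analysed (with three translations and three rotations), and no primary outcome is named. For wire, adjustment is purely a matter of efficiency, and the top of the precision range needs a uniform 1–15 mm spread. Those limits on the finding's reach stand.

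**Conclusion.** The concern holds for Little Index and should be acted on. The direction follows from the design itself: a bounded outcome, a 15-fold range of permitted starting values, non-randomised brackets and no baseline term.

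The size cannot be fixed from the documents. The ligation bias equals the slope of change on baseline multiplied by whatever baseline difference occurs. Under the assumptions shown, a 1 mm difference is enough to raise the false-positive rate well above 5%, and a 0.5 mm difference raises it modestly. The wire comparison remains unbiased in expectation and forgoes precision that is available without cost.

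Adjustment does not make aim 3 a randomised comparison, because it deals only with measured starting severity. Nothing here applies to translation or rotation.

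**What to change.** For Little Index, replace the 3-way ANOVA on change with one model containing wire, period, ligation and the Time Zero Little Index. Let the baseline slope differ by period, and include a patient-level term for the repeated periods. If both arches are analysed, add a term for arch within patient and use the baseline of the same arch. Say openly that this specifies a repeated-measures model, which the plan does not now name for these factors.

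Also:

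- Do not adjust for Time One values, which arise after allocation.
- Report Time Zero Little Index by bracket group, so readers can see whether severity differs.
- State in the limitations that confounding of ligation by clinician or site, and error in the baseline measurement, remain.
- Treat a non-linear baseline term or a wire-by-baseline interaction as optional sensitivity work.

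The cost is a short protocol edit and some analyst time. No extra patients, visits or measurements are needed.

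### The only analysis that names ligation has no baseline term, although bracket type follows faculty preference

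*Combined protocol and SAP*

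**What the plan says.** Possible Limitations states that bracket type cannot be completely randomised, because in the post-doctoral clinic "not all attending faculty members are comfortable using both self-ligating and twin brackets". It concludes: "Bracket type will thus be assigned according to faculty member preference". By contrast, the Methods section describes a random number generator, run by a third party, for the wires.

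Data Analysis computes changes across the three scans in Little's Index and in "translation in three planes, calculated using the superimposition method; and rotation around three axes". It will then "use 3-way ANOVA to evaluate the effect of 3 factors: wire dimension, time, and ligation method". No term for Time Zero irregularity, age, site or clinician is listed. A second analysis is a "repeated measure linear regression model to evaluate any correlation between the degrees of malalignment and the rate of tooth movement". Ligation is not named in it.

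Aim 3 asks for the effect of ligation method, without qualification. The end of the Significance section says "we hope it will provide insight into which archwire dimension and ligation method is ideal for a given patient". Eligibility is wide ("Little Index of 1-15 mm", "Age 10-45 years"), and patients come from a university clinic and a private practice.

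**The concern.** Where treatment follows the clinician's preference, the groups need not be alike at entry, and nothing in the design makes them alike. Expressing the outcome as change from Time Zero does not solve this, because the amount of change available depends on the starting point. An arch that enters at 1 mm can improve by at most 1 mm; one that enters at 15 mm can improve by up to 15 mm. The plan itself expects malalignment to be related to movement, since its second model is built to examine that relation. Yet the comparison of brackets leaves baseline out.

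If bracket groups differed in Time Zero crowding, the ANOVA could report that difference as a ligation effect on Little Index. Aim 3, and the stated hope of informing the choice of ligation method, would rest on that estimate. The hypothesis also makes the wire effect depend on ligation, so the wire-by-ligation result carries the same limit on interpretation.

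**Working it through.** **Inputs from the documents.** 80 patients; two bracket types crossed with two wires; Little Index 1 to 15 mm at entry. The plan gives no derivation of 80 and no alpha, power, SD, correlation, bracket split, number of faculty or intraclass correlation (ICC), so there is no figure to reproduce.

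**Assumed inputs.** Two-sided 5% test, 40 patients per bracket type, baseline SD 3 mm, true ligation effect zero. The correlation r between baseline and change is varied. The highest value corresponds to change = 0.6 × baseline + error with SD 1.5 mm: r = 1.8 / √(1.8² + 1.5²) = 0.77.

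**Step 1: bias without a baseline term.** The spurious ligation difference is slope × gap. With slope 0.6, a 1 mm gap gives 0.6 mm and a 2 mm gap gives 1.2 mm.

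**Step 2: false rejection without a baseline term.** In SD units of change the bias is r × gap / 3. The test is noncentral t on 78 df with noncentrality r × (gap/3) × √20. For a 1 mm gap and r = 0.3 that is 0.3 × 0.333 × 4.472 = 0.447, which gives 7.3%.

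| Gap (mm) | r = 0.3 | r = 0.5 | r = 0.7 | r = 0.77 |
|---|---|---|---|---|
| 0.25 | 5.1% | 5.4% | 5.8% | 5.9% |
| 0.5 | 5.6% | 6.6% | 8.1% | 8.7% |
| 1 | 7.3% | 11.4% | 17.8% | 20.5% |
| 1.5 | 10.2% | 19.7% | 34.0% | 39.6% |
| 2 | 14.3% | 31.3% | 54.0% | 61.9% |

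Simulation of the r = 0.77 case (20,000 runs) gave 20.1% at 1 mm and 61.9% at 2 mm. With baseline as a covariate it gave 4.9% to 5.2% at every gap, for independent patients and baseline as the only confounder.

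**Step 3: the three-factor layout.** With 20 patients per wire-by-ligation cell, two periods (slopes 0.4 and 0.2, period SD 1.06 mm) and ligation tested between patients, 10,000 runs gave 20.3% for ligation at a 1 mm gap unadjusted and 4.7% to 5.4% adjusted across gaps. The wire test stayed at 5.0% to 5.6% and the interaction test at 4.9% to 5.2%.

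**Step 4: precision with no gap.** Detectable difference at 80% power = (t at 0.975 + t at 0.80) × SE. Unadjusted, on 78 df: 2.837 × √(2/40) = 0.634 SD. With baseline, on 77 df, SE = √((2/40)(1 − r²)): 0.605, 0.549 and 0.453 SD at r = 0.3, 0.5 and 0.7.

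**Step 5: what baseline adjustment leaves behind.** If each clinician uses one bracket type and clustering is ignored, the variance is inflated by 1 + (m − 1) × ICC, and false rejection is 2 × (1 − Φ(1.96 / √inflation)). All ICCs and cluster sizes are assumed.

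| Patients per clinician (m) | ICC | Inflation | False rejection |
|---|---|---|---|
| 10 | 0.05 | 1.45 | 10.4% |
| 10 | 0.10 | 1.90 | 15.5% |
| 20 | 0.05 | 1.95 | 16.0% |
| 20 | 0.10 | 2.90 | 25.0% |

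This arises with no baseline gap at all.

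**The case against.** The strongest reply is that the plan already tells the reader what matters. The non-randomised bracket choice and its reason are both stated, effect is ordinary ANOVA vocabulary, and the Significance section only expresses a hope. This stands to a large extent. The disclosure is fair, and the wording of Aim 3 is mainly a reporting matter. What disclosure does not do is change an estimate, and the omitted covariate remains.

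A second reply is that no imbalance is shown. That also stands. The stated reason for bracket choice is clinician comfort, not crowding. A reader might infer that the bracket groups will differ at entry and that the ligation result will be biased; the documents support only that they could differ. With no gap, or a small gap and a weak correlation, the error rate from this source is close to 5%.

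Third, a reader might infer that no bracket allocation is random. The text says that complete randomisation is impossible because part of the study is in the post-doctoral clinic, which leaves open some random allocation elsewhere, although the sentence that follows points to preference throughout.

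Two other defences fail. Change from Time Zero is not baseline adjustment, and the malalignment regression, as written, does not name ligation.

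**Conclusion.** The concern holds as a gap in the analysis: bracket type follows preference, and the only model that names ligation does not adjust for where patients started. It should be fixed because the remedy uses data already planned and gains precision even if the groups turn out alike.

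The possible bias is an illustration, not a finding about this trial. For a 1 mm gap it runs from about 7% to 20% false rejection over the assumed correlations. It applies to Little Index only and says nothing on the size of any bias in the six translation and rotation components.

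Two stronger conclusions are not supported. The wire comparison is not affected in this way if wires are randomly allocated as the Methods section describes. Nor would a baseline covariate make Aim 3 a randomised comparison: it removes only bias from the measured baseline. Ignored clinician clustering could by itself give about 10% to 25% false rejection, under an assumed ICC of 0.05 to 0.10 and 10 to 20 patients per single-type clinician.

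**What to change.** 1. For the Little Index outcome, add Time Zero Little Index and age as covariates in the model that estimates ligation, with patient as the repeated unit.
2. For translation and rotation, use a Time Zero malalignment covariate only if a mapping from the four malalignment types to the six movement components is fixed before outcomes are measured. Otherwise use Time Zero Little Index.
3. Record faculty member and site for each patient, and tabulate bracket type by both.
4. State that ligation and wire-by-ligation results are non-randomised associations wherever brackets followed preference.
5. Fix one rule, including its threshold, before outcomes are measured. If both bracket types occur within enough individual faculty members to estimate it, report the within-faculty ligation contrast. Otherwise report ligation as not separable from clinician, even if both types occur within a site.

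**Cost.** Items 1, 2 and 4 are analysis wording. The Time Zero scan and age are already available, and two covariates use 2 of 80 − 4 = 76 residual df. Baseline adjustment usually narrows the interval. An exception is a large gap with a weak correlation: at 2 mm and r = 0.3, 2.837 × √((2/40 + (2/3)²/78)(1 − 0.09)) = 0.64 SD against 0.63 SD. Item 3 needs two fields per patient. Under item 5, if every faculty member split evenly, the detectable difference would be 0.634 × √(1 − ICC) = 0.62 to 0.60 SD at an assumed ICC of 0.05 to 0.10. It rises as fewer faculty use both types, and where almost none do, Aim 3 can only be described.
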